#### **STOP HCQ block**

- To evaluate the efficacy of chronic (> 3 months) HCQ treatment in chILD compared to placebo.
- To evaluate the safety of HCQ after > 3 months of treatment in chILD.
- To evaluate blood levels of HCQ before and after treatment in chILD.

### 3 TRIAL DESIGN

This study is an explorative, prospective, randomized, double-blind, placebo controlled investigation of hydroxychloroquine (HCQ) in pediatric ILD. The treatments are organized in START and STOP blocks, which can be initiated in sequence, as needed by the subjects. Each patient can participate in each block only once. In the START block subjects are randomized to parallel-groups, then the placebo group is switched to active drug. In the STOP block, subjects on HCQ are randomized into parallel-groups treated with placebo or HCQ to investigate the withdrawal of HCQ for assessment of its efficacy.

#### 3.1 Trial duration and schedule

The duration of this trial is expected to be at least 36 months. The subject recruitment started in Q4 2015 and should last as long as possible, at least till the end of the CHILD-EU project or longer if possible. The actual overall trial duration or subject recruitment period may vary from this time period.

#### 3.2 Number of subjects

It is planned to assess >100 subjects for eligibility and to allocate 80 subjects. Recruitment and treatment of subjects is expected to be performed in up to 100 trial centres. We expect an equal distribution between START and STOP blocks.

#### 3.3 Primary outcome parameters

##### **START HCQ block**

Relative change trial day 1 (i.e. Visit 2) through day 28 (i.e. Visit 3) and relative change day 28 to day 56, (i.e. Visit 4): change active compound compared to change placebo

##### **STOP HCQ block**

Relative change trial day 1 (i.e. Visit 2) through day 84 (i.e. Visit 5): change active compound compared to change placebo

##### Oxygenation

As respiratory condition is also dependent on the support given to the patient this needs to be taken into consideration when assessing oxygenation. Therefore parameters to be measured were defined depending on the patient's condition (Table 3.3-1). How to analyse these variables statistically is detailed in section 8.

Tab 3.3-1: Oxygenation - specific measurements used to determine, depending on Patient's condition

Patient's condition	Measured parameters	Assessment
In room air	In room air O2 Saturation (mean value) Respiratory rate (mean value)	After 5 min at rest room air, then measure twice over 1 minute each, at least 1 min apart
On O2-supplement	In room air O2 Saturation (mean value) Respiratory rate (mean value)	Before O2-withdrawal take same parameters, after 5 min withdraw O2 and obtain steady state O2 Sat in air. Steady state minimum SpO2 should be at least 30 seconds without change. Then measure twice, over 1 minute each, at least 1 min apart. If SpO2 falls below 80%, place back on oxygen.
On high-	O2-flow, air-flow	After 5 min stable rest measure twice over 1 minute

flow nasal cannula		each, at least 1 min apart
Ventilated	Oxygenation index	$OI = (FiO_2 * M_{PAW})/PaO_2$ ; with $FiO_2$ = Fraction of inspired oxygen; $M_{PAW}$ = Mean airway pressure (= ((frequency * inspiration time)/60) * ((inspiratory pressure (PIP) – PEEP) + PEEP)) $PaO_2$ = Partial pressure of oxygen in arterial blood

### 3.4 Secondary outcome parameters

For both, **START** and **STOP** HCQ blocks absolute and relative change under the active compound from trial day 1 (i.e. Visit 2), to START block: day 28 (i.e. Visit 3), STOP block: day 84 (i.e. Visit 5) each, will be compared to change under placebo. The following variables will be investigated:

Oxygen saturation ( $O_2$ -sat, in room air) (only absolute, as relative already primary outcome)  
 Respiratory rate (RR, in room air) (relative and absolute)

Retractions (yes/no)  
 Coughing (yes/no)  
 Oxygen demand

$pO_2$ ,  $pCO_2$  (capillary, in room air)

Chest x-ray

Quality-of-life

Health economics

Overall survival

Weight for height

Cumulative amounts of steroid equivalents. Clinical course of lung disease (since last visit):  
 Healthy/ Sick-better/ Sick-same/ Sick-worse/ Patient died

Pulmonary exacerbation (since last visit)

If  $> 5$  years old (If a child  $\leq 5$  years is already able to perform the listed investigations (spirometry or bodyplethysmography), these should also be performed and documented at the discretion of the investigator.)

The following lung function parameters will be assessed:

FEV1 % predicted (recorded in L), FEV 1 (L), FVC % predicted (recorded in L), FVC (L); MEF 75 (L/s); MEF 50 (L/s); MEF 25 (L/s); TLC (L); ITGV (L); RV (L); R eff (kPa\*s/L); R eff predicted (%).

→ reference values according to the GLI 2012 lung function regression equations

6 minute walking distance (meter)

$O_2$ -saturation before and after 6MWT

Borg scale

If ventilated:

Duration (h) of mechanical ventilation

NO (%), ECMO yes/no, if yes VA/VV, double lumen vs. single lumen, Flow-rate.

### Safety monitoring

Adverse events, clinical laboratory values (GOT, Creatinine, gGT, blood count, differential, LDH, potassium, steady state drug level), ECG, ophthalmologic review

### 3.5 Measures taken to minimize/avoid bias

#### 3.5.1 Randomization

Patients will be allocated to the two treatments, i.e., oral hydroxychloroquine and placebo, in a ratio of 1:1 by central randomization within each age group.

The age-matched stratification will be performed according to 2 age groups defined as infants > 3 Wks, < 2 y and the age category Children > 2 y, because of an anticipated skewed frequency distribution of cases, the older ones being less frequent.

The randomization procedure will not consider the sex of the patients, since no sex-specific responses to HCQ therapy have been reported yet and are not expected. The randomization list will be generated by an independent institute using a validated system, which involves a pseudo-random number generator to ensure that the resulting treatment sequence will be both reproducible and non-predictable.

Only patients who participate in the chILD EU register can be included in the HCQ study. Inclusion in the chILD EU register and in the HCQ study can be performed at the same day.

Patients will not receive a distinct HCQ patient number. The HCQ patient number corresponds to the respective patient number of the chILD EU register.

At screening, each patient to be included will receive the next consecutive random/ patient number from a block of randomization numbers per age group. Study medication will be packed and blinded according to the random list. Each patient medication box will be sent together with the sealed unblinding codes (i.e. envelopes) to the sites. The investigator has to take care that each patient will be provided with the study medication box bearing the correct randomization number.

The randomization list is to be kept confidential and is only accessible to authorized personnel until the code is broken. At the end of the trial, any emergency opening of the envelopes will be controlled after collecting the explanations for unblinding and checking the unused treatment units. The code will be broken regularly only at the end of the study after freezing the statistics database (by checking the data, recording any protocol violations etc.) allowing the collected data to be analyzed.

The randomization list will be kept in safe and confidential custody.

#### 3.5.2 Blinding

Blinding will be achieved by providing the study-specific HCQ-powder/substance and placebo-powder/substance in appropriately covered capsules to keep the content not visible both for the two study drugs hydroxychloroquine and placebo.

In the case of a medical emergency requiring identification of the treatment taken by the patient, the investigator has the right to open the respective envelope, but every effort should be taken to avoid unblinding of patients except the information will be needed for the emergency treatment. Opened envelopes have to be signed, dated and the reason for unblinding has to be documented. The envelope has then to be filed in the ISF and the sponsor and/or the responsible monitor has to be informed. Unblinded patients have to be withdrawn from the study. No other reason than an emergency may justify unblinding. After unblinding the investigator must also note the date, time and reason in the case report form.

### 3.6 Selection and withdrawal of subjects

#### 3.6.1 Inclusion criteria

For block specific inclusion criteria please see synopsis.

Subjects meeting the block specific inclusion criteria and all of the following criteria will be considered for admission to the trial:

1.	
Patients should be clinically stable during baseline (between Visit 1 and 2) for inclusion into the study
 
a) To determine this, attending physicians can use SpO2 in room air for patients on room air or on O2-supplement; the absolute difference on SpO2 is expected not to be <math>\geq 5\%</math> between Visit 1 and 2. For patients on respiratory support, the summary key parameters should not change <math>\geq 20\%</math> between Visit 1 and 2
 
and
 
b) No major changes in other medications between Visit 1 and 2

2.	
Mature newborn <math>\geq 37</math> weeks of gestation, age <math>\geq 3</math> wks and <math>< 2</math>y
 
or
 
Infants and children (<math>\geq 2</math> y and <math>< 18</math> y)
 
or
 
Adults (<math>\geq 18</math> and <math>\leq 30</math> y)
 
or
 
Previously preterm (<math>\leq 37</math> weeks of gestation) babies or children and adults of all ages if chILD genetically diagnosed (see inclusion criterion 3.)

3.	
Diagnosis of chronic (<math>\geq 3</math> wks of duration) diffuse parenchymal lung disease (DPLD = chILD), defined in at least one of the following ways:
 
a) chILD genetically diagnosed
 
Surfactant dysfunction disorders including patients with mutations in SFTPC, SFTPB, ABCA3, TTF1 (Nkx2-1), further extremely rare entities with specific mutations, for example in TBX4, NPC2, NPC1, NPB, COPA, LRBA and other genes. In this case, also previously preterm (<math>\leq 37</math> weeks of gestation) babies or children and adults of all ages can be included into the study.
 
b) chILD histologically diagnosed
 

• Chronic pneumonitis of infancy (CPI)

• Desquamative interstitial pneumonia (DIP)

• Lipoid pneumonitis / Cholesterol pneumonia

• Nonspecific interstitial pneumonia (NSIP)

• PAP after the exclusion of mutations in GMCSF-Ra/b and GMCSF autoantibodies*

• Usual interstitial pneumonia (UIP)

• Follicular bronchitis/ bronchiolitis/ Lymphogenic interstitial pneumonia (LIP)

• Storage disease with primary pulmonary involvement (e.g. Nieman Pick)

• Hermansky Pudlak Syndrome

• Idiopathic pulmonary haemorrhage (haemosiderosis)*

• Other histology diagnosing chILD, in particular combination of the above pattern, but not exclusively

4.	Start block: no HCQ treatment in the last 12 weeks

	Stop block: stable HCQ treatment for at least the last 12 weeks
5.	Ability of subject or/and legal representatives to understand character and individual consequences of clinical trial.
6.	Signed and dated informed consent of the subject (if the subject has the ability) and the representatives (of underaged children) must be available before start of any specific trial procedures.

\*may be diagnosed in the absence of a lung biopsy by characteristic lung lavage cytology (PAS stain, Fe stain), CT pattern or autoantibodies (gliadin, endomysium; cANCA) and clinical course.

### 3.6.2 Exclusion criteria

Subjects presenting with any of the following criteria will not be included in the trial:

- chILD primarily related to developmental disorders
- chILD primarily related to growth abnormalities reflecting deficient alveolarisation
- chILD related to chronic aspiration
- chILD related to immunodeficiency
- chILD related to abnormalities in lung vessel structure
- chILD related to organ transplantation/organ rejection/GvHD
- chILD related to recurrent infections
- Acute severe infectious exacerbations
- Known hypersensitivity to HCQ, or other ingredients of the capsules (lactose-monohydrate, povidone, maize starch, magnesium stearate, hypromellose, macrogol or titanium dioxide (E 171), silicon dioxide or mannitol), to sucrose-octaacetate or sodium saccharine.
- Proven retinopathy or maculopathy
- Glucose-6-phosphate-dehydrogenase deficiency resulting in favism or hemolytic anemia
- Myasthenia gravis
- Hematopoetic disorders
- Pregnancy and lactation (Women with childbearing potential have to practice a medically accepted contraception during trial and till three months after the end of the treatment with HCQ, and a negative pregnancy test (serum or urine) should be existent on Visit 1, if girls of childbearing age and only if sexual relations are known or probable. It is at the discretion and responsibility of the attending physician to decide, whether a pregnancy test is necessary or not. Reliable contraception are systematic contraceptives (oral, implant, injection). Women that are sterile by surgery can participate in the trial. At the discretion of the investigator, sexual abstinence is also accepted as contraceptive method. Girls after menarche have to receive a counselling about birth control methods in presence of at least one parent, which has to be documented in the patient notes.)
- Participation in other clinical trials during the present clinical trial or not beyond the time of 4 half-lives of the medication used, at least one week.
- Hereditary galactose intolerance, lactase deficiency or glucose-galactose-malabsorption
- Renal insufficiency at screening, defined as glomerular filtration rate (GFR)
  - < 40 mL/min/1.73 m^2 in patients age 3 to 8 weeks
  - < 60 mL/min/1.73 m^2 in patients  $\geq$  8 weeks of age  
(KDIGO guideline 2012, K/DOQI guideline 2002)
- Liver disease, gastrointestinal disorder, haematological disorder, epilepsy or other neurological disorder, psoriasis, porphyria at the discretion of the treating physician
- Simultaneous prescription of other potentially nephrotoxic or hepatotoxic medication at the discretion of the treating physician

### 3.6.3 *Withdrawal criteria*

Subjects or/and representatives can withdraw their consent at their own request without given reasons at all time during the trial. This should be without disadvantages for the subject. However the investigator should try to perform a final visit to get concluding findings of investigation.

Subjects may be withdrawn from the trial for the following reasons

- At their own request or at request of the legal representative.
- At the instigation of the sponsor. If, in the investigator's opinion, continuation of the trial would be detrimental to the subject's well-being.
- For women, if it becomes known that the subject is pregnant.
- Aggravation of disease with life threatening events
- Severe side effects (for example retinopathy, cardiomyopathy, ECG-modifications, liver value elevation)
- The subject/ patient is non-compliant or uncooperative
- The subject/ patient is not able to participate due to an Adverse Event
- The subject/ patient has to take any concomitant drugs interfering with the study medication
- The subject/ patient is no longer able to participate for other medical reasons (e.g., surgery, other diseases, or death)

The investigator decides about withdrawal of subjects from the clinical trial in case of occurrence of criteria mentioned above.

In all cases, the reason for withdrawal must be recorded in the CRF and in the subject's medical records. In case of withdrawal of a subject at his/her own request, as far as possible the reason should be asked for and documented. The subject must be followed up and as far as possible; all examinations scheduled for the final trial day should be performed and documented and all trial medication should be collected at site.

All on-going serious adverse events of withdrawn subjects have to be followed up see 7.3.

Withdrawn subjects will not be replaced.

### 3.6.4 *Premature closure of the clinical trial*

The whole trial may be discontinued at the discretion of the sponsor, e.g. for following reasons:

- New risks for subjects become known.
- Inefficacy of the trial medication becomes evident.
- Occurrence of AEs unknown to date in respect of their nature, severity, and duration or the unexpected increase in the incidence of known AEs.
- Medical or ethical reasons affecting disadvantageous the continued performance of the trial.
- Difficulties in the recruitment of subjects.
- The time schedule cannot be met (e.g., more than doubling of recruitment time)
- The sponsor and the investigator decide to discontinue this study because of failure to meet expected goals

The ethic committees (EC) and the competent authorities must then be informed. Should the trial be closed prematurely, all trial material must be returned to or fetched by the monitor.

## 4 TRIAL TREATMENTS

### 4.1 Investigational treatments

#### 4.1.1 HCQ

##### 4.1.1.1 General information about investigational medicinal product (IMP)

International non-proprietary name (INN): hydroxychloroquine

Formulation: Mannitol, Lactose-Monohydrate, Povidon (MW: ca. 25 000), maize starch, Magnesium stearate (Ph. Eur.), Hypromellose, Macrogol (4000), Titanium dioxide (E 171), Silicon dioxide, Sodium saccharine. Capsule

Manufacturer: University Hospital Munich, Pharmacy, [name], Germany.

##### 4.1.1.2 Therapeutic effects

Hydroxychloroquine is an anti-malarial quinolone, which is used in rheumatologic disease as well as in interstitial lung disease. Its mechanism of action in interstitial lung disease is not yet understood. It is believed to change intracellular pH of organelles and affects trafficking of proteins through the cells. Several case reports of children with chILD describe the benefit of hydroxychloroquine either in combination with steroids or alone. This benefit was an improvement of the respiratory condition. In some cases treatment with hydroxychloroquine was successful even after the failure of treatment with steroids.

##### 4.1.1.3 Known important side effects

###### Side effects:

Hydroxychloroquine is considered to be a very safe drug. Nevertheless there is a low risk for several known side effects. The most important side effect is the change of vision.

The incidence of hydroxychloroquine-induced retinopathy is very low with only 2 cases of a series of 400 patients developing irreversible retinopathy, both after having taken maximum dose (400mg) for 6 years. The maximum dose and duration of treatment both appear to have the most impact on the development of retinopathy. Quinolones may also precipitate in the cornea- however this is much less common with hydroxychloroquine than chloroquine.

Further known side effects are

- Gastrointestinal disturbance - nausea, diarrhea, anorexia abdominal cramps.
- Headache
- Skin reactions - rash, pruritus. Rarely pigmentary changes, bleaching of hair and hair loss.
- ECG changes (especially conduction disorders (bundle branch block / atrio-ventricular heart block) as well as biventricular hypertrophy)
- Heart failure, cardiomyopathy in individual cases leading to death
- Severe hypoglycaemia with loss of consciousness
- convulsions
- ototoxicity
- Blood disorders, psychological disturbance, sensomotoric disorders, extrapyramidal disorders, myopathy, Steven Johnson syndrome, acute generalized exanthematous pustulosis, exfoliative dermatitis, photosensitivity, hepatic damage

(according to BSPAR guidance for hydroxychloroquine, October 2010 and Fachinformation Quensyl® January 2017)

For more detailed information please read the current country specific Summary of Product Characteristics of Hydroxychloroquinsulfate (SmPC).

#### 4.1.1.4 Dosage schedule

##### Start HCQ block

During trial: Hydroxychloroquine Sulfate (HCQ) in a loading dose of 10 mg/kg bw/d, p.o., one daily dose in the evening for 7 days, then reduction to 6,5 mg/kg bw/d; the maximum daily dose is 400mg.

##### Stop HCQ block

Individual dose, usually Hydroxychloroquine Sulfate (HCQ) 6 - 10 mg/kg bw/d, p.o., one daily dose in the evening; the maximum daily dose is 400 mg. The dose, on which the patient is included into the trial, should be continued for the duration of the trial.

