## Synopsis

Title	Hydroxychloroquine in pediatric ILD. START randomized controlled in parallel-group, then switch placebo to active drug, and STOP randomized controlled in parallel-group to evaluate the efficacy and safety of hydroxychloroquine (HCQ)
Short title	HCQ in pediatric ILD
EudraCT	2013-003714-40
IZKS trial code	2013-006
Indication	Diagnosed children's interstitial lung disease (chILD) in children and adults
Phase	2a
Treatments	
Test product: Hydroxychloroquine Sulfate (HCQ), one daily dose in the evening.
 
Reference therapy: Placebo
 
The treatments are organized in START and STOP blocks, which can be initiated in sequence, as needed by the subjects.

	START HCQ block
Block specific inclusion criterion (others see 3.6.1)	All subjects not currently on HCQ (last dose $\geq$ 3 months ago) and intention to widen treatment.
Primary objective	To evaluate the efficacy of HCQ after 28 days of treatment in chILD compared to placebo
Secondary objectives	
To evaluate the efficacy of HCQ after 56 days of treatment in chILD compared to 28 days
 
To evaluate the safety of HCQ after 28 and 56 days of treatment in chILD
 
To evaluate blood levels of HCQ after 28 and 56 days of treatment in chILD

Trial design	
Double blinded treatment
 
This is an exploratory Phase 2a, randomized, double-blind, placebo-controlled, parallel-group study and switched placebo to active drug, multicentre, multinational study in subjects with chILD genetically, histologically or clinically diagnosed.
 
This study includes:
 
 
• Screening Period (Day -28 through Day -3)
 
• Treatment Period (Day 1 through Day 56)
 

	STOP HCQ block
Block specific inclusion criterion (others see 3.6.1)	All subjects on chronic (> 3 months) treatment with HCQ (usually 6-10 mg/kg/d or individually tolerated dose) and intention to reduce treatment.
Primary objective	To evaluate the efficacy of HCQ after 84 days of treatment in chILD compared to placebo
Secondary objectives	To evaluate the efficacy of chronic (> 3 months) HCQ treatment in chILD compared to placebo To evaluate the safety of HCQ after > 3 months of treatment in chILD To evaluate blood levels of HCQ before and after treatment in chILD

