The dose given ranged from 3.5 – 10 mg/kg bw/d. In this context it is notable, that there exist two pharmaceutical forms of hydroxychloroquine, the hydroxychloroquine-base and the hydroxychloroquine-sulfate; the correction factor is 200 mg Sulfate = 155 mg Base. The majority of case reports and small series did not indicate which of the two pharmaceutical forms the dose is referring to. In Germany, the common pharmaceutical form is the hydroxychloroquine sulfate and the dose given in chILD is 10 mg/kg bw/d. After extensive discussion with the German competent authorities (BfArM) and the European group of experts, on the basis of available safety data available and possible efficacy, a dose of 6.5 mg/kg b.w./d, after an initial week of treatment with 10 mg/kg b.w./d, was selected for the START study. In the STOP block, the individual dosage, a patient was on until enrollment, should be continued.

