As it is not clear, if HCQ works in these conditions at all, a placebo controlled design is justified. The selected duration of the placebo phase was the result of a delphi questionnaire among European pediatric pneumologists and balanced the anticipated time point, when a treatment effect could be noted in a majority of patients if present, and the time period tolerated to withhold the drug from a placebo treated subject.

So we think, that in a patient with relatively stable disease it is justifiable to start the treatment with the study drug in the placebo arm four weeks later than in the study drug arm without relevant disadvantage for the patient, as till now we don't even know, if he will benefit from the pharmacological treatment or not. Due to this fact, we believe, that all patients should receive HCQ at one point during the study to avoid that patients who might benefit from the treatment with HCQ are not treated.

Due to the heterogeneity of the diseases with a wide spectrum of clinical symptoms and severity it is not possible to determine one specific HCQ treatment duration that will fit the majority of subjects. Physicians anticipate treatment of some patients that will be treated with HCQ only for some weeks and patients that will need HCQ treatment for several years. Due to the variety of conditions and our intention to be as inclusive as possible in this exploratory trial, we decided not to determine the time period patients are treated between the start and stop treatment with HCQ. However, we took the chance to investigate stopping HCQ in a double blind, placebo controlled fashion. As with longer treatment and the intention to terminate treatment the exact time point to stop the treatment does not matter, we suggest a placebo-controlled withdrawal of active drug. In this stop block patients on active drug are randomized in a blinded manner to either continue for three more months with their active treatment or to receive placebo.

In summary the risk of major side effects in these already often used pharmacological treatments as well as the risk of giving placebo instead of the study drug seems acceptable regarding the gain of useful knowledge and the possibility to create adequate treatment strategies for chILD.

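### For patients entering STOP above 400 mg/day, the dose cap and the instruction to continue the entry dose conflict, and the plan does not say which prevails

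*Protocol*

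**What the plan says.** Section 4.1.1.4 of the protocol (Stop HCQ block) describes the dose as "Individual dose, usually Hydroxychloroquine Sulfate (HCQ) 6 - 10 mg/kg bw/d, p.o., one daily dose in the evening" and goes straight on: "the maximum daily dose is 400 mg. The dose, on which the patient is included into the trial, should be continued" throughout the trial.

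Section 1.3 gives the continuation rule without a cap: "In the STOP block, the individual dosage, a patient was on until enrollment, should be continued". Section 1.4 describes the randomised choice in STOP in the same spirit: patients "continue for three more months with their active treatment or to receive placebo". Section 4.1.6 adds that doses need no adjustment during the trial.

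On eligibility, the synopsis criterion for STOP asks for more than 3 months of HCQ, "usually 6-10 mg/kg/d or individually tolerated dose". Criterion 4 in section 3.6.1 reads "Stop block: stable HCQ treatment for at least the last 12 weeks". Neither sets an upper limit in mg, and the exclusion criteria in 3.6.2 set none. Section 3.6.1 admits adults up to 30 years, and "children and adults of all ages if chILD genetically diagnosed". There is no weight limit.

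**The concern.** For a patient who enters on more than 400 mg/day, continuing the entry dose and staying within the maximum cannot both be done. The text does not say which instruction gives way.

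STOP is a randomised withdrawal comparison. Its reference condition is an unchanged dose after at least 12 weeks of stable treatment. If the cap is applied at randomisation, affected patients in the HCQ arm move to a lower dose, so for them the comparison is reduced dose against placebo. If the response depends on dose, the contrast shrinks. If the entry dose is kept instead, the patient exceeds a maximum that the protocol itself states.

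The planned analysis would not show which had happened. HCQ entry dose is not among the baseline variables in SAP section 4.1. Compliance in SAP section 6.5 counts capsules, not mg. SAP section 2.3 drops the per-protocol analysis.

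**Working it through.** The plan gives no derived figure on this point, so there is nothing to reproduce. The check asks whether the conflict can arise within the protocol's own dose range, and how large a reduction would be if the cap prevailed.

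**Inputs**

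- Maximum daily dose in STOP: 400 mg (section 4.1.1.4).
- Usual individual dose: 6 to 10 mg/kg of the sulfate (section 4.1.1.4). Section 1.3 gives 10 mg/kg as the dose used for chILD in Germany.
- Body weight: not given. The weights below are assumptions.

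**Step 1. Weight above which the entry dose passes the cap**

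Threshold weight = 400 / (dose in mg/kg).

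- 10 mg/kg: 400 / 10 = 40.0 kg
- 8 mg/kg: 400 / 8 = 50.0 kg
- 6 mg/kg: 400 / 6 = 66.7 kg

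At or below 40 kg no dose in the usual range passes 400 mg, and the two instructions agree. The range is only described as usual, so an individually tolerated dose outside it could behave differently.

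**Step 2. Reduction on day 1 if, and only if, the cap overrides the entry dose**

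Reduction = 1 − 400 / (weight × mg/kg).

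| Weight (assumed) | Entry dose per kg | Entry dose | Reduction to 400 mg |
|---|---|---|---|
| 45 kg | 10 mg/kg | 450 mg | 11% |
| 50 kg | 10 mg/kg | 500 mg | 20% |
| 60 kg | 6 mg/kg | 360 mg | none |
| 60 kg | 8 mg/kg | 480 mg | 17% |
| 60 kg | 10 mg/kg | 600 mg | 33% |
| 70 kg | 6 mg/kg | 420 mg | 5% |
| 70 kg | 8 mg/kg | 560 mg | 29% |
| 70 kg | 10 mg/kg | 700 mg | 43% |

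**Step 3. What each reading of section 4.1.1.4 implies**

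| Reading | Consequence for entry above 400 mg/day |
|---|---|
| The cap prevails | Dose reduction on day 1 in the HCQ arm; departs from 1.3 and from the description of the active arm in 1.4 |
| Continuation prevails | The stated maximum is exceeded |
| The cap limits which entry doses are admissible | Nobody is reduced, but the synopsis criterion and sections 3.6.1 and 3.6.2 do not contain the limit |

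Each reading leaves at least one passage needing a change.

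**Step 4. Scale within the block**

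With 80 patients and an equal split expected between blocks (section 3.2), STOP would have about 40. Each affected patient is then 1/40 = 2.5% of the block. With 1:1 allocation, about half of those affected would be in the HCQ arm. How many there are cannot be derived from the documents.

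**The case against.** The strongest counter-argument is that section 4.1.1.4 can be read coherently. The first sentence defines the individual dose, including its maximum; the second holds the dose at inclusion constant. On that reading nobody is reduced. Section 4.1.1.3 also refers to 400 mg as the maximum dose when it describes retinopathy. This reading is open, but it does not close the gap: section 1.3 points to the dose taken before enrolment, and no eligibility criterion carries the limit.

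The number affected may be small or zero. Section 3.5.1 expects older patients to be less frequent, and patients above 40 kg belong to that group. No document reports a patient entering above 400 mg/day, and the German 10 mg/kg is not said to be given uncapped to heavier patients. The larger reductions arise at the top of the dose range; at 6 mg/kg nobody up to 66.7 kg is affected. All of this stands, and it limits the size of the point.

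Three stronger inferences are tempting and are not supported:

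- A reader might infer that the HCQ arm has a dose cut on day 1. No passage says so. It follows only if the cap prevails.
- A reader might take the synopsis as repeating the continuation rule. It contains only an entry criterion and a figure label for the individual dose.
- A reader might expect different pharmacists to resolve the conflict differently. Sections 4.1.1.1, 4.1.5 and 4.1.6 describe a single hospital pharmacy that makes, packs and ships the capsules.

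It is also true that treatments in the 3 months before entry are to be recorded and that HCQ levels are measured during STOP. The raw information may therefore exist, but the SAP does not use it for this purpose.

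**Conclusion.** The point holds as a contradiction confined to patients who enter STOP above 400 mg/day. The protocol's own dose range and age limits make such patients eligible, above 40 to 66.7 kg depending on mg/kg, and the documents do not say which instruction governs them.

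If the cap governs, the day-1 reduction in affected HCQ-arm patients runs from about 5% (70 kg, 6 mg/kg) through 20% (50 kg, 10 mg/kg) to 43% (70 kg, 10 mg/kg), at assumed weights. The effect on the responder comparison cannot be sized: the number affected is unknown, any dose-response is unknown, and a capped patient still receives 400 mg against placebo. The half-lives given in section 1.3 would also delay the effect of a reduction. The claim that the block is biased towards no effect therefore goes too far. What can be said is that the contrast could be narrowed by an unknown amount.

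Confidence is high for the conflict in the text and low for any effect on the results. It should be fixed because the correction is small and the analysis as planned would not reveal the problem.

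**What to change.** **Protocol.** Reconcile the synopsis criterion for STOP, section 1.3, criterion 4 in section 3.6.1 and section 4.1.1.4, so that one rule covers entry doses above 400 mg/day and is settled before randomisation, whether through dosing or through eligibility. Which rule applies is the sponsor's clinical decision, and no view is taken here.

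**Data.** Record for every STOP patient the entry dose in mg and in mg/kg, and the dispensed dose. Express the entry dose as the sulfate: section 1.3 notes that sulfate and base differ (200 mg to 155 mg) and that reports often do not say which is meant, so an unspecified dose could fall on the wrong side of the limit.

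**SAP.** Add a baseline flag for an entry dose above 400 mg/day, defined in the same way in both arms, and repeat the STOP responder comparison of section 6.6 without flagged patients as a sensitivity analysis. The flag should not be defined by a difference between dispensed and entry dose. Placebo patients receive no HCQ, so that definition would remove the whole placebo arm; applied to the HCQ arm alone, it would break the randomised comparison. A flag fixed by entry dose avoids both problems.

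**Cost.** A few sentences in the protocol, one derived variable and one table. The sensitivity analysis has fewer patients, in a block expected to hold only about 40. If enrolment is already complete, the flag and table can still be added before unblinding.
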